#### 5.4.1.2. Coding of Reported Terms

All AE terms will be coded in the database using the MedDRA version 21.0 or higher coding dictionary.

All tables in this section will show the AE terms coded into PT grouped into body SOC. Subject listings will also show the reported terms. Any other coding levels will only be shown in a listing summarizing coding or if explicitly mentioned.

#### 5.4.1.3. Allocation of Adverse Events to Analysis Periods

All AEs records will be placed into analysis periods considering their start date, aiming to report the incidence of these events only in the analysis period during which they started.

The general rule for allocation of AEs to analysis periods follows:

Analysis period start date  $\leq$  AE start date  $\leq$  analysis period end date

If the start date of an AE is missing or incomplete to a level preventing a clear allocation of the AE to one single analysis period and no flag indicating timing relative to study medication is available, a worst-case consideration (see below) will be done aiming to allocate the AE to one single analysis period, if possible. When a worst-case consideration is needed, the end date of the AE, if and as available, should also be considered; if such AEs clearly end on a given point, this will exclude the possibility to allocate the AE to an analysis period after that point.

- 
- An AE which according to the available information of its start date could belong to the screening as well as to the treatment period will only be placed in the treatment period.
  - An AE which according to the available information of its start date could belong to treatment period as well as to follow-up period will only be placed in the treatment period.
  - An AE with a missing start date will be allocated to treatment period.
  - If an AE can be allocated to both double-blind and open-label (i.e. CL-206 study) treatment period based on the above rules, then the event will be reported for CL-204 double-blind treatment period during CL-204 study analyses.

#### **5.4.1.4. Treatment Relatedness**

Following ICH-E3 (ICH), the originally reported relatedness to IMP of an AE will be dichotomized as follows:

- *Not IMP related*: all non-missing weaker levels of relatedness than ‘possibly IMP related’.
- *IMP related*: ‘possibly IMP related’ and all stronger levels of relatedness (this class also includes any missing IMP relatedness, as a worst-case consideration).

Only this dichotomized relatedness will be used in tables. Relatedness as originally reported will only be listed.

#### **5.4.1.5. Presentation of Adverse Events and of Event Episodes**

All AEs tables will only show TEAEs and will show counts of the number of subjects with TEAEs. The number of event episodes will be shown only in tables where explicitly mentioned.

AEs starting before first IMP administration or later than 30 days after the last dose of IMP but before first OLE IMP administration (not TEAEs) will only be listed. AEs reported on or after the date of first OLE IMP administration will be included in the CSR produced after CL-206 study has been completed.

AEs leading to death will be presented in a separate listing.

#### **5.4.1.6. Worst-Case Selections**

When cross-tabulating AE preferred terms versus an AE attribute (like severity), only the worst-case within each same preferred term, same subject and same analysis period will be considered, i.e., when a same subject has more than once the same AE preferred term reported in the same treatment group, the subject will be counted only once and will be shown under the worst outcome (like the worst severity for that AE in the concerned treatment period).

---

#### **5.4.1.7. Calculation of Relative Days and Duration**

For each AE record, its start day in study (the day of the AE start date relative to the date of first IMP administration), its start day in the analysis period, and its duration (in days) will be calculated and shown only in listings.

See sections [3.3.1](#) and [3.3.2](#) for the calculation of relative days and duration respectively.

#### **5.4.1.8. Presentation of Results**

A summary table will be provided, showing then number (percentage) of subjects with:

- at least one TEAE,
- at least one IMP-related TEAE,
- any serious TEAE,
- any TEAE leading to death,
- any TEAEs by worst severity,
- TEAE leading to IMP discontinuation.

Frequency tabulations, by SOC and PT, of the number (percent) of subjects with a TEAE will be presented by treatment group. Similar tables will be provided for the following groups:

Severity ('Grade 1 - Mild', 'Grade 2 – Moderate', 'Grade 3 – Severe', 'Grade 4 – Life Threatening', and 'Grade 5 – Death')

- Related TEAEs
- Related TEAEs by severity
- Serious TEAEs.

Serious adverse events, AEs leading to death, AEs leading to IMP and trial discontinuation will be listed.

#### **5.4.1.9. EudraCT Adverse Events Reporting**

For the purpose of EudraCT reporting, the following tabulations will be added:

Frequency tabulations, by SOC and PT, of the number (percent) of subjects with non-serious TEAE will be presented. A similar table will be provided for the all serious TEAEs (counting events), as well as a table for non-serious TEAEs reported in at least 5% of the subjects in any treatment group.

Urinalysis tests will be presented as part of the descriptive statistics tables.

Results of serology testing, pregnancy test, and FSH will only be listed.

### 5.4.3.2. Derivation Rules

#### Fasted and Non-Fasted Results

Laboratory parameters that are sensitive to the fasting status: glucose, triglycerides.

These parameters will be tabulated with descriptive statistics by fasting/non-fasting and toxicity grade. Laboratory results for which the fasting status is missing, will be considered as taken non-fasted.

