  - AST or ALT  $\geq 3x$  ULN with signs of severe liver damage (i.e. with the appearance of fatigue, nausea, vomiting, right upper quadrant pain or tenderness, fever, rash and/or eosinophilia [ $>5\%$ ], and/or total bilirubin  $\geq 1.5x$  ULN or international normalized ratio [INR]  $>1.5$ ).
  - AST or ALT  $\geq 3x$  ULN for more than 2 weeks.
- Clinical laboratory test suggestive of cholestasis with total serum bile acid levels  $>3x$  ULN on a sample taken in fasted state (at least 8 hours fasted). If the routine random or postprandial total serum bile acid sample is  $>3x$  ULN, then the subject should have a fasted sample taken within 1 to 5 days. The results of this test will determine whether the subject should discontinue IMP or not.

When test results need to be confirmed, the subject should return to the clinical study center and be evaluated as soon as possible, preferably within 48 hours from awareness of the abnormal results. This evaluation should include laboratory tests, detailed history, and physical assessment. In addition to repeating AST and ALT, laboratory tests should include albumin, creatine kinase, total bilirubin, direct and indirect bilirubin, gamma glutamyl transferase (GGT), INR, and alkaline phosphatase. A detailed history, including relevant information, such as review of ethanol, recreational drug and supplement consumption, family history, sexual history, travel history, history of contact with a jaundiced subject, surgery, blood transfusion, history of liver or allergic disease, and work exposure, should be collected. Further testing for acute hepatitis A, B, or C infection and liver imaging (e.g. biliary tract) may be warranted. All cases confirmed on repeat testing with no other cause for LFT abnormalities identified at the time should be considered potential Hy's Law cases irrespective of availability of all the results of the investigations performed to determine etiology of the abnormal LFTs. Such potential Hy's Law cases should be reported as SAEs.

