### 6.6.2. Clinical Laboratory Evaluations

The following clinical laboratory safety tests will be performed:

- Hematology: hematocrit, mean corpuscular volume, mean corpuscular hemoglobin, mean corpuscular hemoglobin concentration, hemoglobin, red blood cell count, white blood cell count, white blood cell differential count (absolute and relative), and platelets.
- Coagulation: INR, thromboplastin time, and partial thromboplastin time.
- Serum/plasma chemistry: random glucose, urea, creatinine, uric acid, sodium, potassium, calcium, chloride, phosphorus, AST, ALT, GGT, total bilirubin, alkaline phosphatase,

lactate dehydrogenase, total serum bile acid, albumin, total proteins, triglycerides, cholesterol (total, low density lipoprotein, and high density lipoprotein), creatine kinase, and C-reactive protein.

- Urinalysis:
  - Dipstick: pH, glucose, proteins, blood, leucocytes, ketones.
  - Microscopic examination of the sediment (cylinders, erythrocytes, leucocytes) if indicated.
- Serology: hepatitis B surface antigen, hepatitis C virus antibody, and HIV-1 and HIV-2 antibodies (only at screening). Positive hepatitis and HIV results should be reported by the investigator as required by local law.
- FSH test for females at screening to confirm menopause if applicable.
- Pregnancy test for females: serum beta human chorionic gonadotropin at screening, urine pregnancy test on a monthly basis (only for WOCBP).

The clinical laboratory evaluations will be performed at visits specified in the Schedule of Activities in Section 6.11 (see also Section 6.1, “[Timing of Assessments](#)”). Reference ranges will be supplied by the central laboratory. Clinical laboratory values outside the normal range will be flagged and clinical relevance will be assessed by the investigator. Only laboratory test abnormalities judged as clinically significant by the principal investigator should be recorded as AEs.

The details of blood and urine sample handling and shipment instructions will be provided in a separate laboratory manual.

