### **Selection of Visits**

Per parameter, analysis visit and timepoint, the value closest to the target date will be used in analysis tables and figures. Other values will be listed only. If more than one value is located at the same distance from the target day, then the latest in time will be selected. If there are two values on the same day and no time indicating which one is last, the average of the two will be calculated.

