##### **Non-graded Abnormalities**

The following worst-case post-baseline abnormalities L, N or H will be determined per subject, per parameter and for the on-treatment analysis period, using all non-missing post-baseline records within that period (including unscheduled and follow-up visits):

- L = low: at least one post-baseline result is classified as L.
- N = normal: all post-baseline results are classified as N.
- H = high: at least one post-baseline result is classified as H.

If, for a subject, both L and H are reported, the subject will be counted twice in the table: once with a worst-case L and once with a worst-case H.

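### The SAP does not treat total serum bile acids as fasting-sensitive, so the worst-case and treatment-emergent tables count meal-related highs and do not show the protocol's fasted >3x ULN criterion

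*SAP*

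**What the plan says.** **Protocol.** Section 6.6.2 puts bile acid in the routine chemistry panel ("lactate dehydrogenase, total serum bile acid, albumin, total proteins, triglycerides"). Section 4.5.4 makes it a laboratory criterion for stopping IMP: a total serum bile acid above 3x ULN "on a sample taken in fasted state (at least 8 hours fasted). If the routine random or postprandial total serum bile acid sample is" above that same multiple, "then the subject should have a fasted sample taken within 1 to 5 days". The fasted result then decides whether IMP is stopped.

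**SAP, fasting status.** Section 5.4.3.2 states "Laboratory parameters that are sensitive to the fasting status: glucose, triglycerides". What follows from being on that list is limited: "These parameters will be tabulated with descriptive statistics by fasting/non-fasting and toxicity grade". Missing status is covered too: "Laboratory results for which the fasting status is missing, will be considered as taken non-fasted".

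**SAP, classification.** Bile acid has no row in Table 4 and is not among the four parameters categorized separately below it (prothrombin time, fasting glucose, HDL, LDL). By 5.4.3.4 it is therefore classed low, normal or high (L/N/H). Under 5.4.3.6 a post-baseline H is treatment-emergent if the baseline class was different or missing. Under 5.4.3.7, "H = high: at least one post-baseline result is classified as H", and unscheduled and follow-up samples count. Section 5.4.3.9 feeds these classes into the shift table and the treatment-emergent frequency table. Table 5 (hepatotoxicity) covers AST, ALT and bilirubin only.

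**SAP, by-visit tables.** Section 3.3.4 applies a different rule: "the value closest to the target date will be used in analysis tables and figures. Other values will be listed only". Ties go to the later sample.

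**The concern.** The protocol does not act on a non-fasted bile acid value by itself; the SAP summarizes such values as if meal state were irrelevant. Two things follow in the worst-case and treatment-emergent tables. A high caused by a recent meal enters as a treatment-emergent abnormality and stays there after a normal fasted repeat. And the finding that matters clinically, a fasted value above 3x ULN, gets the same H as a fed value just over the limit. The separate listing of subjects with a grade 3 or higher value does not help, because bile acids carry no grade.

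The readout matters for this compound. Protocol 2.1.3 does not rule out an interaction with the bile salt export pump, and 2.1.4.1 reports minimal bile duct hyperplasia in dogs. Safety is the secondary objective, and with 20 and 10 subjects a few spurious flags change how the table reads.

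**Working it through.** The plan gives no figure on this point. Its one design figure (63%, protocol 7.1) concerns mRSS and plays no part here.

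**1. Trace one subject through the rules.** Baseline N; routine random sample above 3x ULN; fasted repeat a few days later N.
- Protocol 4.5.4: the fasted repeat is below the threshold, so the criterion is not met.
- SAP 5.4.3.4: classes are N (baseline), H (random), N (repeat).
- SAP 5.4.3.6: the H differs from baseline, so it is treatment-emergent.
- SAP 5.4.3.7: one H is enough, so the worst case is H. The repeat is included but cannot lower it.

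A high between 1x and 3x ULN triggers no repeat under the protocol, so nothing is available to set against it. Conversely, a meal-related H at baseline hides a later H.

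**2. By-visit tables.** The repeat is used if it is nearer the target day than the random sample, or tied. Assume the visit day is uniform within the protocol window and the repeat comes 1 to 5 days later with equal chance. Let d be the visit's offset from target and k the delay; the repeat is used when |d + k| ≤ |d|.
- ±2-day window (Weeks 2 and 4): 6 of 25 combinations = 24%.
- ±4-day window (Weeks 8, 16 and 24): 16 of 45 combinations = 36%.

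So the repeat sometimes enters these tables, as an accident of timing.

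**3. Possible size.** The documents give no rate of meal-related highs. Assume probability p per sample, the same at baseline, independent between samples, with no drug effect. The Schedule of Activities has five on-treatment laboratory visits after baseline (Weeks 2, 4, 8, 16, 24).
- Worst case H: 1 − (1 − p)^5
- Treatment-emergent H (baseline not H): (1 − p) × [1 − (1 − p)^5]

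| p (assumed) | Worst case H | Treatment-emergent H | Expected of 20 / of 10 |
|---|---|---|---|
| 5% | 22.6% | 21.5% | 4.3 / 2.1 |
| 10% | 41.0% | 36.9% | 7.4 / 3.7 |
| 20% | 67.2% | 53.8% | 10.8 / 5.4 |
| 30% | 83.2% | 58.2% | 11.6 / 5.8 |
| 40% | 92.2% | 55.3% | 11.1 / 5.5 |

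The treatment-emergent share peaks near p = 30% and then falls, because more baselines are already H. Counting Follow-up Visit 1 as a sixth sample gives 25.2% at p = 5% and 61.8% at p = 30%.

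Independence drives these figures. If the same subjects tend to be high at every visit, their baseline is H as well and the treatment-emergent share falls, towards zero in the extreme.

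**The case against.** **The SAP does not override the stopping rule.** A reader might infer that the two documents contradict each other on who stops IMP. They do not: 4.5.4 governs the individual decision, and SAP 5.4.3 only summarizes. A confirmed case that stops IMP also reaches the adverse event tables, through protocol 9.1.5 and the SAP 5.4.1.8 summary of events leading to IMP discontinuation. This stands.

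**The repeat is not lost everywhere.** A reader might infer that a normal fasted repeat can never count. That is true only of the worst-case and treatment-emergent tables. By-visit tables can pick it up, and the listings show every value.

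**Fed samples are likely but not shown.** Inclusion criterion 9 mentions fasting laboratory tests, though for eligibility. Visit-day blood is drawn before IMP, and a subject could be bled first and then eat and dose. Against this, 4.5.4 itself calls the routine sample random or postprandial, and 6.6.2 lists random glucose. The rate remains unknown, so the inference that the table would measure meal timing more than drug effect is not supported.

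**A fasted-only table could be worse.** If routine samples are mostly non-fasted, fasted samples come mainly from subjects selected for a random value above 3x ULN. Under SAP 3.5.3 the denominator would shrink to that group. Many might lack a fasted baseline, and a missing baseline makes any H treatment-emergent. This stands and limits the fix.

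**Some SAP text is not visible.** Section 5.4.2, most of 5.4.3.1 and the text of 5.4.7 (listed in the contents as covering meal intake) cannot be read, and derivation details sit in a separate document. A bile-acid rule there cannot be excluded. The fasting-sensitive list and Tables 4 and 5 are visible and contain none.

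**Conclusion.** The point holds for the worst-case and treatment-emergent tables. As visible, the SAP ignores fasting status for a parameter whose fasted value the protocol makes decisive, and no planned table shows the protocol's own bile-acid criterion.

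Both arms share the rule and no p-values are planned for laboratory data. The consequence is background noise that can dilute a real signal or make one hard to read; it does not favour an arm, and it does not affect individual stopping decisions. The 22% to 58% range is an illustration resting on an assumed 5% to 40% per-sample rate, equal at baseline, and on independence between samples. Within-subject consistency would lower it. The rule trace in step 1 needs none of these assumptions.

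**What to change.** - In SAP 5.4.3.2, add total serum bile acids to the fasting-sensitive parameters.
- State that both the descriptive statistics and the L/N/H results for bile acids are presented by fasted and non-fasted status. Adding the name alone is not enough, because the present rule splits only descriptive statistics and toxicity grades, and bile acids have no grade.
- Keep the all-sample worst-case table. Do not replace it with a fasted-only table or let the repeat overwrite the random value, given the selection problem above.
- Add two rows to Table 5, by arm, with all treated subjects who have post-baseline bile-acid data as denominator: (a) any total serum bile acid above 3x ULN; (b) above 3x ULN on a sample fasted at least 8 hours, which is the protocol 4.5.4 criterion as written.

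The cost is SAP wording and a little programming; the SAP already handles fasting status, including missing status. The fasted cells will be sparse, which is a further reason to keep the all-sample table. No clinical rule changes.

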### 5.4.3.3. Definition of Toxicity Grades

Toxicity grades will only be derived for laboratory tests for which toxicity gradings are available.

For the analysis values of the following continuous laboratory parameters, toxicity grades will be determined as implemented in the next table (Common Terminology Criteria for Adverse Events (CTCAE), v5.0: November 27, 2017). Analysis results scoring below the lowest grade limits are defined to correspond to grade 0.

**Table 4: Laboratory Toxicity Grades**

Parameter	Direction of abnormal	Grade 1	Grade 2	Grade 3	Grade 4
Alanine amino transferase	high	>ULN-3 x ULN	>3 x ULN -5 x ULN	>5 x ULN - 8 x ULN	>8 x ULN
Albumin (g/L)	low	<LLN-30	<30-20	<20	-
Alkaline phosphatase	high	>ULN-2.5 x ULN	>2.5 x ULN -5 x ULN	>5 x ULN -20 x ULN	>20 x ULN
Aspartate amino transferase	high	>ULN-3 x ULN	>3 x ULN -5 x ULN	>5 x ULN -8 x ULN	>8 x ULN
Bilirubin [total]	high	>ULN-1.5 x ULN	>1.5 x ULN -3 x ULN	>3 x ULN -10 x ULN	>10 x ULN
Calcium, below (mmol/L)	low	<LLN-2.0	<2.0-1.75	<1.75-1.5	<1.5
Calcium, above (mmol/L)	high	>ULN-2.9	>2.9-3.1	>3.1-3.4	>3.4
Cholesterol (mmol/L)	high	>ULN-7.75	>7.75-10.34	>10.34-12.92	>12.92
Creatine kinase	high	>ULN-2.5 x ULN	>2.5 x ULN -5 x ULN	>5 x ULN -10 x ULN	>10 x ULN
Creatinine	high	>ULN-1.5 x ULN	>1.5 x ULN -3 x ULN or >1.5 x baseline -3 x baseline	>3 x ULN -6 x ULN or >3 x baseline	>6 x ULN
eGFR/ Creatinine clearance	low	<LLN-60	<60-30	<30-15	<15

Parameter	Direction of abnormal	Grade 1	Grade 2	Grade 3	Grade 4
(mL/min/1.73 m  )					
Eosinophils absolute count	high	>ULN	-	-	-
Eosinophils relative count (%)	high	>7	-	-	-
Gamma-glutamyl transferase	high	>ULN-2.5 x ULN	>2.5 x ULN -5 x ULN	>5 x ULN -20 x ULN	>20 x ULN
Glucose [fasting], below (mmol/L)	low	<LLN-3.0	<3.0-2.2	<2.2-1.7	<1.7
Hemoglobin, below (g/L)	low	<LLN-100	<100-80	<80	-
Hemoglobin, above (g/L)	high	Increase >0-20	Increase >20-40	Increase >40	-
Lymphocytes, below (10  /L)	low	<LLN-0.8	<0.8-0.5	<0.5-0.2	<0.2
Lymphocytes, above (10  /L)	high	-	>4.0-20.0	>20.0	-
Neutrophils, below (10  /L)	low	<LLN-1.5	<1.5-1.0	<1.0-0.5	<0.5
Potassium, below (mmol/L)	low	<LLN-3.0	-	<3.0-2.5	<2.5
Potassium, above (mmol/L)	high	>ULN-5.5	>5.5-6.0	>6.0-7.0	>7.0
Sodium, below (mmol/L)	low	<LLN-130	<130-125	<125-120	<120
Sodium, above (mmol/L)	high	>ULN-150	>150-155	>155-160	>160
Triglycerides fasting and non-fasting (mmol/L)	high	>1.71-3.42	>3.42-5.7	>5.7-11.4	>11.4
Partial thromboplastin time [activated or not specified]	high	>ULN-1.5 x ULN	>1.5 x ULN -2.5 x ULN	>2.5 x ULN	-
International normalized ratio	high	>1.2 x ULN -1.5 x ULN	>1.5 x ULN -2.5 x ULN	>2.5 x ULN	-
Platelets (10  /L)	low	<LLN-75	<75-50	<50-25	<25
White blood cells, below (10  /L)	low	<LLN-3	<3-2	<2-1	<1
White blood cells, above (10  /L)	high	-	-	>100	-
Legend: [Specifications]. (Specific unit into which the defined grades apply). Baseline value is defined as abnormal if the value is not within the normal range. For directional toxicity of high an abnormal baseline will be a baseline value which is higher than the upper limit of the reference range. For directional toxicity of low, an abnormal baseline will be a baseline value which is lower than the lower limit of the reference range. x LLN / x ULN = times the lower / times the upper limit of the normal range. Below / above = differentiate grade definitions in the low / high sense for a same parameter.					

---

The following parameters will be analyzed and categorized based on pre-defined criterion without using the above defined grading system:

- Prothrombin time: >ULN-1.5 x ULN; >1.5 x ULN - 2.5 x ULN; >2.5 x ULN
- Glucose [fasting] (mmol/L): >7.2
- High density lipoprotein (mmol/L): <1.554
- Low density lipoprotein (mmol/L): >4.144

The analysis of these parameters will be performed in the same way as the analysis of the parameters with standard toxicity grade.

#### **5.4.3.4. Definition of Non-Graded Abnormalities**

Non-graded abnormalities will be determined only for the parameters having no definitions of toxicity grades (see section [5.3.3.3](#)).

For laboratory tests provided by the laboratory, the position of the actual analysis values versus their normal ranges will be determined directly by using the position indicator provided in the database as reported, expressing the classes for these analysis values as low (L), normal (N) or high (H). L, N and H are further referred to as non-graded abnormalities.

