#### **5.4.3.6. Treatment Emergent Principle**

##### **Toxicity Grades**

A post-baseline toxicity grade 1, 2, 3 or 4 is defined as treatment-emergent when higher than the toxicity grade of the baseline result. If the baseline result is missing, a post-baseline toxicity grade 1, 2, 3 or 4 will always be considered as treatment-emergent.

For prothrombin time parameter a post-baseline value meeting the defined abnormality criteria is regarded as treatment-emergent if the post-baseline criteria meet a higher degree of abnormality than the baseline value (e.g. post-baseline value meeting >1.5-2.5 x ULN category while baseline meeting >ULN-1.5 x ULN category) or the baseline value is missing or does not meet any abnormality criteria. For glucose [fasting], high density lipoprotein and low density lipoprotein a post-baseline abnormal category will be regarded as treatment emergent, if the baseline value is missing or does not meet the defined abnormality criteria.

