##### **Non-graded Abnormalities**

A post-baseline non-graded abnormality class L or H is defined as treatment-emergent when it differs from the abnormality class of the baseline result. If the baseline result is missing, a post-baseline abnormality L or H will always be considered as treatment-emergent.

---

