#### 5.4.3.8. Elevated Liver Function Test

To assess the potential of the IMP to cause severe liver damage, possible Hy's Law cases will be identified. Count and percentage of subjects who have at least one assessment meeting the criteria defined in [Table 5](#) will be summarized in the on-treatment analysis period.

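### Total serum bile acid has a protocol stopping limit of 3x ULN, but the visible SAP laboratory tables class it only Low, Normal or High, so crossings of that limit are not counted by arm

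*SAP*

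**What the plan says.** Protocol 6.6.2 includes total serum bile acid in the routine chemistry panel. Protocol 4.5.4 gives as a reason to stop study drug a "Clinical laboratory test suggestive of cholestasis with total serum bile acid levels" above 3x ULN in a sample fasted for at least 8 hours. A random or post-meal value above 3x ULN leads to a fasted retest within 1 to 5 days, and the retest decides.

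SAP 5.4.3.3 grades the parameters in Table 4 and gives separate cut-offs for prothrombin time, fasting glucose, HDL and LDL. Bile acid is in neither list. The fallback in SAP 5.4.3.4 is "Non-graded abnormalities will be determined only for the parameters having no definitions of toxicity grades", using Low, Normal or High against the laboratory range.

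Three rules then apply to non-graded parameters:

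- Treatment-emergent (5.4.3.6): "A post-baseline non-graded abnormality class L or H is defined as treatment-emergent when it differs from the abnormality class of the baseline result". A missing baseline also counts.
- Worst case (5.4.3.7): "H = high: at least one post-baseline result is classified as H".
- Shift and frequency tables (5.4.3.9) are built from these classes.

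SAP 5.4.3.8 promises "Count and percentage of subjects who have at least one assessment meeting the criteria defined in" Table 5, which covers AST, ALT and bilirubin only. On fasting, SAP 5.4.3.2 states "Laboratory parameters that are sensitive to the fasting status: glucose, triglycerides"; bile acid is not named.

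**The concern.** The SAP gives other numeric stopping limits of the protocol their own table categories. Table 5 has AST/ALT at 3x and 8x ULN, and bilirubin at 1.5x ULN combined with AST or ALT at 3x. Table 6 has QTcF above 500 ms and a change above 60 ms. Bile acid also has a stopping limit but gets no matching category.

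Bile acid is of some interest for this compound. Protocol 2.1.3 does not rule out an interaction with the bile salt export pump, and Protocol 2.1.4.1 reports liver cell infiltrates and minimal bile duct hyperplasia in dogs at 150/100 mg/kg/day.

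What is at stake is whether a reader of the laboratory tables can see, by arm, how many subjects passed 3x ULN, and whether a marked rise in a subject who began slightly above normal is flagged. Neither the primary endpoint nor the protection of subjects during the trial depends on it.

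**Working it through.** The plan states no figure on this point, so there is none to reproduce. The check applies the written rules.

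**Step 1: where bile acid lands.** It is not in Table 4, not among the four parameters with separate cut-offs, and not in Table 5. The Low/Normal/High rule of 5.4.3.4 is the only visible one left.

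**Step 2: the SAP rule against a tiered rule.** The comparison is the SAP's own treatment of prothrombin time. Its categories are "Prothrombin time: >ULN-1.5 x ULN; >1.5 x ULN - 2.5 x ULN; >2.5 x ULN", and a value "is regarded as treatment-emergent if the post-baseline criteria meet a higher degree of abnormality than the baseline value", or if baseline is missing or not abnormal. For bile acid the tiers would be >ULN to 3x ULN and >3x ULN.

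| Baseline | Worst post-baseline | SAP label | Treatment-emergent, SAP | Treatment-emergent, tiered |
|---|---|---|---|---|
| Not High | >ULN to 3x | H | yes | yes |
| Not High | >3x | H | yes | yes |
| >ULN to 3x | >ULN to 3x | H | no | no |
| >ULN to 3x | >3x | H | **no** | **yes** |
| >3x | >ULN to 3x | H | no | no |
| >3x | >3x | H | no | no |
| Missing | >ULN to 3x | H | yes | yes |
| Missing | >3x | H | yes | yes |

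The treatment-emergent flag differs in 1 of 8 cells. In all 4 cells with a worst value above 3x ULN, the SAP label is the same H as for a value just above ULN.

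**Step 3: example values (assumed, in multiples of ULN).**

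- 0.8 to 1.1 and 0.8 to 3.5 both go from Normal to High, are both treatment-emergent, and share one table cell.
- 1.2 to 3.5 and 2.5 to 6 both go from High to High. Neither is treatment-emergent under the SAP; both are under the tiered rule.
- 1.2 to 1.5 is not treatment-emergent under either rule.

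**Step 4: how many subjects.** The number missed by the flag in an arm is

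N × (share with High baseline of at most 3x ULN) × (share of those who then exceed 3x ULN).

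N is 20 active and 10 placebo (Protocol 7.1). The documents give neither share. If the first is assumed to be 0%, 10%, 20% or 30%, the subjects who could not be flagged whatever their rise number 0, 2, 4 or 6 of 20 and 0, 1, 2 or 3 of 10. Those are subjects at risk of being missed, not crossings. If 10% of them cross, a 10% share gives 20 × 0.10 × 0.10 = 0.2 active and 10 × 0.10 × 0.10 = 0.1 placebo. A 30% share gives 20 × 0.30 × 0.10 = 0.6 and 10 × 0.30 × 0.10 = 0.3.

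**Step 5: what other outputs show.**

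- By-visit statistics include the maximum (SAP 3.5.2, 5.4.3.9), but use one value per visit, the one closest to the target day (SAP 3.3.4). A peak at an unscheduled visit can be absent, and a maximum is not a count.
- The extra listing for CTCAE grade 3 or higher cannot be triggered by bile acid, which has no grade.
- The full laboratory listing holds every value with its normal range, so a hand count is possible.

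**The case against.** The strongest reply is that the SAP delivers what the protocol promised. Protocol 7.3.6.3 asks for descriptive statistics, changes from baseline and shifts against normal ranges, and Low/Normal/High shifts are that. This stands: there is no contradiction between the documents.

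Second, the event that matters for decisions is a confirmed fasted value above 3x ULN, which stops treatment. Discontinuation reasons are tabulated by arm (SAP 5.2.2). Under Protocol 9.1.5, an abnormality that leads to discontinuation is recorded as an adverse event if it meets the definition, and so should reach the count of events leading to discontinuation (SAP 5.4.1.8). This largely stands. A reader might infer that subjects who reached the stopping limit vanish from the report, and the documents do not support that. What remains uncounted is mainly unconfirmed, non-fasted values above 3x ULN.

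Third, a reader might take the 6 of 20 in Step 4 as the number missed. It is an assumed share of High baselines, not a number of crossings. High baselines are also probably uncommon: inclusion criterion 9 refers to fasting laboratory tests and requires out-of-range results to be judged not clinically significant.

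Fourth, a High that stays High after a Normal fasted retest may look like a bile acid error. It is the SAP's conservative convention for every non-graded parameter.

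Finally, SAP 5.4.2 and most of 5.4.3.1 are not visible, and SAP section 1 places the mock tables in a separate document. A bile acid category could exist there. The conclusion that the plan as a whole lacks one is therefore not available. Table 4, the list of other cut-offs, Table 5 and the classification rules are visible, however, and they are what the point rests on.

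**Conclusion.** The point holds as a minor one. Under the visible rules, bile acid is the parameter with a protocol stopping limit that is reduced to Low/Normal/High. As a result, no visible laboratory table counts subjects above 3x ULN by arm, and one of eight baseline-to-worst transitions, from a High baseline of at most 3x ULN to above 3x ULN, is not flagged as treatment-emergent.

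The number of subjects affected is unknown and probably small. With about 30 subjects, the count can be made from the listings. The effect is confined to the by-arm laboratory safety summary. The conclusion assumes that the redacted text and the mock tables add no bile acid category.

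**What to change.** In SAP 5.4.3.3, add total serum bile acid to the parameters with pre-defined criteria, with categories >ULN to 3x ULN and >3x ULN. In 5.4.3.6, apply the prothrombin-time rule to it, against the Day 1 baseline taken before dosing.

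Report the worst-case on-treatment count above 3x ULN by arm, as a separate row or a small footnoted table alongside Table 5. Keep it apart from the Hy's Law criteria, because that section serves to identify possible Hy's Law cases from AST, ALT and bilirubin. Footnote that the Protocol 4.5.4 stopping limit applies only to fasted samples. Split the count by fasting status only if that is recorded for bile acid samples, which the visible text does not confirm; otherwise give one unsplit count.

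The cost is a few lines of SAP text and slightly more table programming. The main count needs no new data. The drawbacks are small cell counts and a possible mismatch between a fasted baseline and a non-fasted later sample (or the reverse), which could create or hide a treatment-emergent flag.
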